Mexico is going through a major environmental and nutritional crisis, which is related to unsustainable dietary behaviors. Sustainable diets could solve both problems together. However, in Mexico and the world, an intervention program oriented to promoting sustainable diets has not been designed. This study protocol aims to design a 3-stages, 15 weeks, sustainable-psycho-nutritional digital intervention program whose objective is to promote the adherence of the Mexican population to a sustainable diet and to evaluate its effects on dietary water and carbon footprints, metabolic biomarkers, and gut microbiota of this population. The behavior change wheel model and the guide for digital interventions design will be followed. In stage 1, the program will be designed using the sustainable diets model, and the behavior change wheel model. A sustainable food guide, sustainable recipes, and food plans as well as a mobile application will be developed. In stage 2, the intervention will be carried out for 7 weeks, and a follow-up period of 7 weeks, in a sample of Mexican young adults (18 to 35 years) randomly divided into an experimental group (n=50) and a control group (n=50). The nutritional care process model will be used. Anthropometric, biochemical, clinical, dietary, environmental, socioeconomic level and cultural aspects, nutritional-sustainable knowledge, behavioral aspects, and physical activity will be considered. Thirteen behavioral objectives will be included using successive approaches in online workshops twice a week. The population will be monitored using the mobile application that will include behavioral change techniques. In stage 3, the effects of the intervention will be assessed on the dietary water and carbon footprint, lipid profile, serum glucose, and gut microbiota composition of the evaluated population. We expected to find improvements in health outcomes and a decrease in the dietary water and carbon footprints. With this study, the first theoretical-methodological approach to the sustainable-psycho-nutrition approach will be generated.

Keywords: Sustainable Diets, Behavior Change, Gut Microbiota, Environmental Impact of Diets, Nutritional and Environmental Education, Mexican Population, Water Footprint, Carbon Footprint, Eating Behavior, m-Health.

1. Introduction

The change from the traditional Mexican diet to a Western diet, generated by the nutritional transition, has not only generated prevalence's of more than 75% of metabolic alterations (obesity, type 2 diabetes, cardiovascular diseases, dyslipidemia) (1–3) and in the gut microbiota of the Mexican population (4), but it has also generated the water and carbon footprint of their diet to be the highest in the world with more than 8,000 Liters per person per day ($L\ p^{-1}d^{-1}$) (5) and 6.01 Kg $CO^2eq\ p^{-1}d^{-1}$ (6), respectively. This is linked to the aggravation of climate change, with increases of more than 1.0 °C in the average atmospheric temperatures (7) and the current water crisis that Mexico is going through, which affects 85% of the territory and has been referred to as the worst water drought in history, affecting the water supply of millions of Mexicans (1,8).

One of the proposals for the joint solution of these problems has been the adoption of sustainable and territorial diets, which in Mexico could be carried out through the recovery of its traditional diet, both pre-Hispanic and colonized, which, prepared with low-fat culinary techniques and low content of animal products, can be considered as an appropriate option from a nutritional, cultural, economic and environmental perspective, dimensions that must be present for a diet to be considered as sustainable (1,9–12).

However, to achieve the adoption of a particular diet, it is necessary to modify the eating behavior of the population (13–15). To modify both dietary and unsustainable behaviors in a population, there are multiple strategies, among which intervention programs have stood out (14,16,17). However, to date and both nationally and internationally, no intervention program whose objective is to promote both adequate nutrition to improve health and reduce the environmental impact of dietary behaviors, has been reported. This respecting cultural, social, economic, and psychological aspects of the population.

Based on the above, this study protocol aims to design a three-stage 15 weeks intervention program, based on the guide to designing interventions of the behavior change wheel model (14), which includes both nutritional and sustainability elements, in the sense of considering unsustainable dietary behaviors of the Mexican population, in addition to taking into account their social, cultural and economic aspects. In addition to these axes, the basis of behavioral modification intervention programs is psychology. Therefore, it is proposed to design a sustainable-psycho-nutritional intervention program, whose objective is to promote the adherence of the population to sustainable diets. But, in addition, it is proposed to evaluate its effects on environmental indicators, metabolic biomarkers, and gut microbiota, as well as clinical aspects and body composition in a Mexican population sample. Because of the effectiveness of technologies use in nutritional (18,19) and environmental (20,21) interventions,

the intervention program will be a digital one, for which a mobile application is being designed to evaluate and monitor the intervened population. Therefore, this will be a m-Health intervention program.

We hypothesized that a sustainable-psycho-nutritional intervention digital program can modify the eating behavior of a Mexican population group and guide it towards a sustainable diet, generating decreases in glucose levels, total cholesterol (TC), LDL cholesterol (LDL-C), and triglycerides (TG), and increases in HDL cholesterol (HDL-C) levels. Likewise, we hypothesized that this type of program can modify the composition of the gut microbiota of the population, promoting the proliferation of bacteria related to metabolic health; reduce the water and carbon footprint of the sample's diets; maintain adequate body fat levels in the population with an adequate body fat percentage or reduce them in the overweight or obese population; maintain blood pressure levels in the healthy population and lower them in the population with high blood pressure, and reduce the presence of acanthosis nigricans.

2. Methods

It is proposed to carry out a quasi-experimental longitudinal study of three stages that will be related to each other.

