2.2 Stage 2: Application of the sustainable-psycho-nutritional intervention program

2.2.1 Participants

Once the intervention program has been designed, it will be applied to a sample of Mexican young adults from the south of Jalisco, randomly divided into two groups: an experimental group (n=50) and a control group (n=50). This is based on recommendations for group designs in behavior modification programs (38). The sample size is according to the minimum suggested for nutritional interventions (39,40), and taking into account the possible desertion of the participants during the intervention, which can amount to more than 50% of the initial sample (41). We will include a population between 18 and 35 years old, with Body Mass Index (BMI) values from 18.5 to 40, with or without risk factors for the development of chronic diseases, but without diagnosis with previous pharmacological treatment. The inclusion, exclusion, and elimination criteria are detailed in Supplementary Material 2 in Table SM2.1. Also, for being included in the study cut-off points to identify inadequate consumption and physical activity were established (Table SM2.2). The population will be invited to participate through social networks and posters at strategic points, such as Universities, gyms, and the downtown city. Young adults were selected as the population for this study since they are already considered adults who make autonomous food decisions, but at the same time, their young age makes them susceptible to behavioral modification. In addition, they represent parents or future parents, as well as the active population of Mexico, so providing nutritional-sustainable education to these people could generate long-term benefits for their health and that of their families (21,42,43).

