2.3.4 Statistical analyses

The distribution of the data will be analyzed with the Kolmogorov Smirnov test. Descriptive analysis will be performed, including means, standard deviations, and medians. Next, the effects of the program on the selected variables will be assessed by comparing them between evaluations and between groups with t-student tests for paired and unpaired data, respectively, if a normal distribution is found. For no normally distributed data, the Wilcoxon test (repetitive measures) and the U de Mann Whitney test (independent groups) will be used. For no categorical variables, the chi-squared test will be used. Correlation analyses will also be performed, considering Pearson correlation for normally distributed data and Spearman correlations for no normally distributed data. Likewise, simple, and multiple linear regression models will be carried out, as well as binary logistic regression analysis, to identify relationships and risks between variables. Statistical analysis will be performed at STATA V12® program.

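### Body-fat and blood-pressure hypotheses depend on baseline status, but the planned effect tests name no baseline stratum, interaction or adjustment, and no criterion for maintenance

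*Combined protocol and SAP*

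**What the plan says.** The last paragraph of section 1 states two hypotheses whose direction depends on where a participant starts. For body fat, the program should "maintain adequate body fat levels in the population with an adequate body fat percentage or reduce them in the overweight or obese population". For blood pressure, it should "maintain blood pressure levels in the healthy population and lower them in the population with high blood pressure".

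Section 2.2.1 recruits a mixed sample: BMI from 18.5 to 40, with or without risk factors, 50 per group. Table SM2.1 excludes hypertension only when it is medicated, so untreated raised blood pressure can enter.

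Section 2.3.4 says that the effects of the program "will be assessed by comparing them between evaluations and between groups with t-student tests for paired and unpaired data, respectively". For non-normal data, "the Wilcoxon test (repetitive measures) and the U de Mann Whitney test (independent groups) will be used". The section also states that "simple, and multiple linear regression models will be carried out, as well as binary logistic regression analysis, to identify relationships and risks between variables", but it names no outcome, covariate, arm term or interaction for those models.

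No section defines an analysis by baseline body fat or blood pressure, adjusts for the baseline value, or states what result would count as levels having been maintained. Section 2.2.3 refers to the Mexican norm for blood pressure measurement, but no cut-off is written out. For body fat percentage no reference is given at all.

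**The concern.** Each hypothesis makes two claims, and the tests named for program effects fit neither well.

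- **Reduction in the elevated.** If the effect exists only in participants who start high, a comparison of whole arms averages it with a zero effect in everyone else. A real fall can be missed.
- **Maintenance in the healthy.** This is a claim of no material change. A difference test can reject equality but cannot establish it. With small strata, a worsening that matters can easily be non-significant.

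Because the classification is not fixed in advance, anyone who later wants to address the hypotheses must choose cut-offs after the data are in. The obvious shortcut would be a paired test within those who started high, and that would show a fall from regression to the mean even if the program did nothing.

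**Working it through.** **The plan's own figure.** Section 2.2.1 gives 50 per group, based on a minimum from cited studies. It states no alpha, power, effect size or SD, so the figure cannot be reproduced. For orientation (two-sided alpha 0.05, 80% power, normal approximation), the detectable difference is (1.960 + 0.842) × √(2/n): 0.56 SD at n = 50 and 0.79 SD at n = 25.

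**Inputs from the documents.** 50 per arm. Dropout may exceed 50% of the initial sample (section 2.2.1), and non-completers are eliminated (Table SM2.1), so 25 per arm is a plausible analysed number.

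**Assumptions.** Effect d = 0.7 SD in the elevated and zero in the rest; share elevated f = 0.5 or 0.3; two-sided alpha 0.05; SD of change in blood pressure 8, 10 or 12 mmHg. The documents supply none of these. The share may well differ between body fat and blood pressure.

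**Dilution.** The pooled effect is f × d: 0.5 × 0.7 = 0.35 SD, or 0.3 × 0.7 = 0.21 SD. Power comes from the two-sample t-test with non-centrality effect × √(n/2). The pooled test uses n per arm and the stratum test uses f × n per arm.

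| n per arm | Share elevated | Pooled: effect, power | Stratum: n per arm, power |
|---|---|---|---|
| 50 | 0.5 | 0.35, 41% | 25, 68% |
| 50 | 0.3 | 0.21, 18% | 15, 46% |
| 25 | 0.5 | 0.35, 23% | 12.5, 39% |
| 25 | 0.3 | 0.21, 11% | 7.5, 24% |

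For the first row, the non-centrality is 0.35 × √25 = 1.75 pooled and 0.7 × √12.5 = 2.47 in the stratum. The calculation ignores the small extra spread that mixing the strata creates, which slightly favours the pooled test.

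**Maintenance.** Take half the sample as healthy and let the experimental group's blood pressure rise by 5 mmHg relative to control. The standardised shift is 5/SD: 0.625, 0.50 and 0.42.

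| Healthy per arm | SD 8 | SD 10 | SD 12 |
|---|---|---|---|
| 25: chance of p > 0.05 | 42% | 59% | 70% |
| 12.5: chance of p > 0.05 | 68% | 78% | 83% |

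At 25 per arm the 95% confidence interval half-width is 4.5, 5.7 and 6.8 mmHg, so intervals of this width would often include the 5 mmHg rise.

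**What the trial could support instead.** An equivalence test (one-sided alpha 0.05, 80% power, true difference zero) with an assumed 0.5 SD margin needs 2 × ((1.645 + 1.282)/0.5)² ≈ 69 healthy participants per arm, more than a whole arm. The arm-by-status interaction, 0.7 against 0 with 25 per cell, has standard error √(4/25) = 0.40 SD, non-centrality 0.7/0.40 = 1.75 and about 41% power, the same as the pooled test.

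**The case against.** Several stronger readings are tempting, and the documents do not support them.

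- *The plan will treat non-significance as maintenance.* It never says so. The supportable statement is that it gives no criterion, and its effect tests cannot supply one.
- *The plan commits to one pooled test.* Section 2.3.4 is silent on strata. Pooling is what follows if it is applied as written, not a stated decision.
- *Only difference tests are planned.* Linear and logistic regression are also listed. Their stated purpose is to explore relationships and risks, with no arm-by-status term, so they do not fill the gap as written. They do show that the tools are at hand.
- *A paired test within elevated participants is planned.* It is not. Regression to the mean is a warning about a likely shortcut.
- *Neither half of the hypothesis can be answered.* This is too absolute: a diluted between-arm contrast still carries some information about reduction.

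Two further objections have force. Body fat and blood pressure are absent from the effects that the abstract lists for stage 3, although section 1 includes clinical aspects and body composition in its aims and hypotheses. And stratifying does not rescue power: after 50% dropout the stratum test reaches only 24–39% under these assumptions, and the interaction test is no stronger than the pooled one. The case for the change is that it estimates the quantity hypothesised, not that it makes these hypotheses well powered.

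**Conclusion.** The point stands as a mismatch between hypothesis and analysis. The hypotheses differ by baseline status, the sample is mixed, and the tests assigned to program effects carry no stratum, interaction or baseline adjustment. Followed as written, the plan yields a diluted contrast for reduction and no valid evidence for maintenance.

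The direction of the dilution follows from the plan's own hypothesis. Its size rests wholly on the assumed effect, share and SD, because the documents provide none. The ranking of stratum over pooled power holds in all four scenarios shown; the absolute levels fall sharply once the plan's own dropout expectation is applied. This should be corrected, but it concerns outcomes outside the abstract's main list and does not threaten the trial's other comparisons.

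**What to change.** In section 2.3.4:

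1. Prespecify the baseline classification. For blood pressure, take it from the Mexican norm already cited in section 2.2.3. For body fat, name a reference before analysis, since none is written.
2. For each outcome, fit one model of the follow-up value on arm, baseline value, baseline status and arm-by-status interaction.
3. Report the between-arm difference with its 95% confidence interval in each stratum.
4. State that p > 0.05 in the healthy stratum will not be reported as maintenance; the interval shows which changes remain compatible with the data.
5. State that within-group paired change in an elevated stratum will not be taken as evidence of effect. The randomised control comparison guards against regression to the mean.
6. Label the stratum results exploratory, because neither the interaction nor an equivalence claim is adequately powered.

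The cost is analysis-plan wording, a classification to define and justify, and wider intervals within strata. The required body-fat and blood-pressure measurements are already planned, so no extra visits or participants are needed.

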2.1 Stage 1: Design of the program

A sustainable-psycho-nutritional intervention program will be designed based on the characteristics of a sustainable diet for the national context of Mexico, adaptable to any regional context. It will include a mobile application that is being designed for this project, which will include a sustainable food guide, sustainable-psycho-nutritional workshops, sustainable recipes and food plans, and behavioral change techniques. The program will be designed based on the sustainable diets model (12) and concept (9), the behavior change wheel model (14), the guideline for the development and evaluation of digital behavioral interventions in health care (19), and on the guide to designing interventions of the behavior change wheel, which incorporate 3 stages and 8 development steps (22).

2.1.1 Mobile application design

A mobile application (app) will be developed in collaboration with software and mobile applications developers and will be based on the user-centered methodology (23), and on the guide for the design of digital interventions by West and Michie (24). It will contain the following behavioral modification techniques: education

through workshops videos (13); persuasion by sending messages of risks and benefits (25), encouragement and coercion using token economy (13), nudges by messaging (26), self-monitoring by graphical progress viewing (27,28), successive approaches by behavioral objectives addressing (13), and guides (14), through a sustainable food guide that will be designed by means of linear programming optimization (29,30) using MATLAB®, and graphic design programs such as Adobe Illustrator® and BioRender®. This guide will be designed based on the recommendations of the FAO for the development of dietary guidelines (31) and on the Mexican Food Equivalent System (32). For the token economy system, cut-off points will be established to be charged to the app (Supplementary Material 1). Additionally, educational workshops and meal plans will be designed, following the model of sustainable diets of Johnston et al. (12), and using the Nutriecology® Nutritional-Ecological software and the Nutrimind® Software for diet calculation. Likewise, the guidelines for the prescription of meal plans, menu design, and recipes for the Mexican population will be followed (33). Prior to the launch of the mobile application, its feasibility, acceptability, quality, and usability will be assessed. Also, it will be evaluated following the APEASE criteria, which include evaluating the 1) Affordability, 2) Practicability, 3) Effectiveness, and Cost-effectiveness, 4) Acceptability, 5) Side-effects/safety, and 6) Equity.

2.1.2 Behavior change intervention design process

The process of design of the intervention is shown in Table 1. The process of understanding the behavior, including the problem definition (1–3,5,6), the selected target behaviors, and what needs to be modified from them (12,13,27,34–36) are described. Also, the selected intervention functions (37), as well as the selected policy categories from the behavior change wheel model, are presented.

Table 1. Design of the Sustainable-Psycho-Nutritional intervention program according to the behavior change wheel model and guide for interventions design

Stage 1: Understand the behavior	
Step 1: Define the problem in behavioral terms	This step will be based on the available scientific evidence on the country's dietary and environmental situation, which reveals high prevalence's of overweight, obesity, and associated pathologies such as type 2 diabetes, dyslipidemia, and hypertension (1,2,6). Also, the highest values of dietary water and carbon footprints were found (5,6). These problems are mainly related to inadequate food consumption (which will be further detailed) and lack of physical activity (1).
Step 2: Select target behavior	The target behaviors will be lack of physical activity performance, inadequate consumption of Mexican foods and dishes, fruits and vegetables, whole grains, legumes, seeds and healthy fats, dairy products, eggs, fish and shellfish, chicken, red meat (beef and pork, and, in some cases, goat and lamb) and processed, ultra-processed foods and added and free sugars, as well as foods high in trans and saturated fats.
Step 3: Specify the target behavior	Targets behaviors will be established as a goal-setting strategy, which has been reported to be one of the most effective methods for modifying dietary behaviors (27). Also, they will be addressed as successive approximations toward a sustainable diet, another effective behavior change technique (13,33). Targets behaviors will be:
Step 4: Identify what needs to change	
 1. Increase physical activity. 2. Increase the consumption of sustainable Mexican foods and dishes. 3. Increase the consumption of fruits and vegetables. 4. Increase the consumption of whole grains. 5. Increase the consumption of legumes. 6. Increase the intake of seeds and healthy fats. 7. Reduce dairy consumption. 8. Reduce the consumption of eggs. 9. Reduce consumption of fish and shellfish. 10. Reduce chicken consumption. 11. Reduce the consumption of red (beef, pork, goat, and lamb) and processed meats. 12. Reduce the consumption of ultra-processed foods. 13. Reduce the intake of added and free sugars, as well as foods with a high content of trans and saturated fats. 
All foods whose consumption will be promoted will be aligned with the sustainability characteristics for the Mexican context (12), on the recommendations of a healthy diet provided by the WHO (35), and on the model QC7G for food and nutrition education, that will specify which foods to select, in which quantities, when to consumed them and how to prepare them. In addition to when to perform physical activity, specifying type and duration (13).

Stage 2: Identify intervention options	
Step 5: Intervention functions	The intervention functions from the behavior change wheel model will be: education, persuasion, incentivization, and coercion. These will be verified in relation to the APEASE criterion Michie et al. (36).

Table 1. Continuation: Design of the Sustainable-Psycho-Nutritional intervention program according to the behavior change wheel model and guide for interventions design

Stage 2: Identify intervention options	
Step 6: Policy categories	
The policy category of the behavior change wheel model will be the guidelines. Therefore, a nutritional-sustainable food guide will be designed, using linear programming optimization (29, 30), based on the FAO recommendations for the development of dietary guidelines (31), and covering the elements of the sustainable diets model (12) as follows: 1) Wellness and Health: ABCD; A: anthropometric and body composition data (body weight and height, BMI, percentage of body fat, visceral fat, muscle mass, waist, and hip circumference, as well as waist-hip ratio); B: biochemical data (serum glucose, lipid profile and gut microbiota); C: clinical data (signs of nutrient deficiencies, acanthosis nigricans, and blood pressure). 2) Biodiversity, environment, and climate: carbon footprint and gray water footprint. 3) Equity and fair trade: food prices and socioeconomic level of the population. 4) “Eco-friendly”, local, and seasonal foods: green and blue water footprint, locally produced and seasonal foods. 5) Cultural heritage and skills: Traditional Mexican diet, Mexican Diet Quality Index Adapted (IACDMx), and nutritional education based on a traditional diet. 6) Food needs, nutrients, food security, and access: personalized food plan according to individual requirements, preferences, and contexts. Figure 1 shows an adaptation of the model of sustainable diets of Johnston et al. (12) for this protocol characteristics.
 
Subsequently, this nutritional-sustainable food guide will be accompanied by a system of equivalent foods (32) that, in addition to incorporating the food's nutrients, will integrate their environmental impact. The calculation of the environmental impact will be made based on the calculation of the total, green, blue, and gray water footprint, using the Water Footprint Assessment method for Mexico (5). Likewise, the greenhouse gas emissions of foods will be calculated, using the Life Cycle Assessment method for food production and processing through pre-quantified databases (55,56,57). The prices and cultural characteristics of the main consumed foods in Mexico will be included (5,32). Prices will be obtained based on fieldwork in supermarkets, and a review of supermarket databases, while cultural aspects will be determined based on a literature review of the traditional Mexican diet (1,10).
 
Once sustainability dimensions are calculated, a sustainable recipe book will be developed, including examples of food plans with individualization options. These food plans will be made up of a distribution of equivalent food rations (32) and examples of menus that meet the nutritional and sustainability characteristics of the Mexican population, with adaptations options.

Stage 3: Identify content and implementation options	
Step 7: Behavior change techniques	
Specific behavior change techniques will be used covering the selected intervention functions as follows:
 
 • Education: successive approximations in the workshops addressing the target objectives. • Persuasion: Nudges, risk, and benefits communication. • Incentivization, coercion, and monitoring: messaging, remainders, and token economy through food registers by writing and photos on the mobile application. • Social support: forum in the mobile app where participants can share pictures of their foods and their physical activity performance. Also, will be able to like the photos of other participants and comment on the photos. Also, a chat for the resolution of doubts between user and administrator will be included in the mobile application.
Step 8: Mode of delivery	The mode of delivery will be digital since a mobile application is being designed and the workshops will be delivered by digital platforms in videos.

[figure not shown]

Figure 1. Sustainable-Psycho-Nutritional approach for the intervention design, based on the sustainable diets model (12), The behavior change wheel model (14), and the COM-B model (14). Own elaboration.

